9.4.19 Total Gonadotropin Dose, Number of Stimulation Days, and Number of Dose Adjustments

The analysis strategies are described in Section 8.1.1.

10 Safety

10.1 General Considerations

Analyses for the safety analysis set will be conducted according to the actual treatment received.

Data will be presented by summary tables and listings. Categorical data will be summarized by treatment using the number and percentage of subjects in each category. For calculation of percentages, the denominator will be the total number of subjects in the respective treatment group in the safety analysis set. Continuous data will be summarized by treatment using number, mean, standard deviation, median, minimum, and maximum.

All individual subject data will be listed per subject and treatment as observed including any derived values.

Missing Data

Missing values will be treated as missing, except for causality, intensity, seriousness, and outcome of adverse events. A worst-case approach will be used: if causality is missing, the adverse event will be regarded as related to the IMP; if the intensity of an adverse event is missing, the adverse event will be regarded as severe; if seriousness is missing, the adverse event will be regarded as serious; if outcome is missing, and no date of outcome is present, the outcome is regarded as 'ongoing'.

10.2 Adverse Events

Adverse events will be coded using MedDRA using the version effective at trial start. Adverse events will be grouped according to start of IMP as follows:

- Pre-treatment adverse event, i.e. any adverse event occurring after signed informed consent and before start of IMP, or a pre-existing medical condition that worsens in intensity after signed informed consent but before start of IMP.
- Treatment-emergent adverse event in the fresh cycle, i.e. any adverse event occurring after start of IMP and before the end-of-cycle visit, or a pre-treatment adverse event or pre-existing medical condition that worsens in intensity after start of IMP and before the end-of-cycle visit.
- Adverse events in cryopreserved cycles, i.e. any adverse event occurring after initiation of a cryopreserved cycle and before the end-of-cycle visit, or a pre-existing medical condition that worsens in intensity after initiation of a cryopreserved cycle and before the end-of-cycle visit.

Treatment-emergent adverse events and adverse events in cryopreserved cycles will be presented in summary tables and listings. Separate summary tables will be produced for treatment-emergent adverse events in the fresh cycle and adverse events in cryopreserved cycles cumulatively (overall and by programmed and natural cycles separately). Summaries will also be provided for the trial across fresh and cryopreserved cycles.

Pre-treatment adverse events will be presented in a listing only.

Treatment-emergent adverse events will be tabulated by system organ class alphabetically and PT in decreasing order of frequency. The following will be presented: number of subjects reporting an adverse event, the percentage of subjects with an adverse event, and the number of events reported.

Summary tables will be produced for the following: all treatment-emergent adverse events, treatmentemergent adverse events by causality (reasonable possibility / no reasonable possibility), treatmentemergent adverse events leading to death, adverse events by intensity (mild / moderate / severe), treatment-emergent adverse reactions by intensity (mild / moderate / severe), serious treatmentemergent adverse events, serious treatment-emergent adverse reactions, treatment-emergent adverse events leading to discontinuation, treatment-emergent adverse events with an incidence of \geq 5% in any treatment group, treatment-emergent adverse reactions with an incidence of \geq 5% in any treatment group, and non-serious treatment-emergent adverse events with an incidence of \geq 5% in any treatment group.

Similar displays will be prepared for the adverse events in cryopreserved cycles. Listings of adverse events in the cryopreserved cycles will indicate whether or not the adverse event occurred before, during, or after the COVID-19 pandemic trial hold.

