6.1.12 End-of-cycle

If a subject attends the scheduled trial visits, the end-of-cycle assessments should take place at the last scheduled cycle visit, i.e. for subjects with a confirmed vital pregnancy, the ongoing pregnancy visit will be the last scheduled cycle visit and thus the visit where the end-of-cycle assessments should be done.

Due to the timing of the mandatory anti-FSH antibody assessments, the end-of-cycle assessments can at the earliest be performed 21-28 days after the last FE 999049 or placebo dose. This may coincide with the β hCG visit for subjects with a negative β hCG test.

The following must take place at the end-of-cycle visit, irrespective of whether the subject discontinues the trial prematurely or completes it:

- Body weight
- Physical examination
- Gynecological examination
- Vital signs (systolic blood pressure, diastolic blood pressure, pulse)
- Blood collection for central laboratory analysis of:
 - clinical chemistry and hematology parameters
 - anti-FSH antibodies (second post-dosing assessment) [note: only applicable for subjects who have not already had a blood sample taken for the second post-dosing anti-FSH antibodies assessment as described in section 6.1.9.2]

Trial Code: 000002 Date: 25 Apr 2018 E-Study Protocol-22377; Ver. 1.0

Supersedes: None Page 82 of 159

- Drug accountability, if applicable
- Recording of use of any concomitant medication
- Recording of adverse events
- Complete end-of-cycle form

These assessments serve to document the subject's physical health at the end of the cycle.

Trial Code: 000002 Date: 25 Apr 2018 E-Study Protocol-22377; Ver. 1.0

> Supersedes: None Page 83 of 159

6.2 **Cryopreserved Cycles**

The trial covers cryopreserved cycles initiated within 12 months from the start of controlled ovarian stimulation. Either a programmed cycle (section 6.2.1) or a natural cycle (section 6.2.2) can be selected for any cryopreserved cycle.

6.2.1 **Programmed Cryopreserved Cycles**

The flow of the trial procedures in the programmed cryopreserved cycles initiated within 12 months from the start of controlled ovarian stimulation is shown in Table 6-3.

Table 6-3 Trial Flow Chart - Subject and Blastocyst Procedures - Programmed Cryopreserved Cycles Initiated Within 12 Months From the Start of Controlled **Ovarian Stimulation**

	Preparation of the endometrium			Transfer	Pregnancy monitoring			End

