8.3.2 Pregnancy Losses

The following terminology should be used for reporting of pregnancy losses as adverse events:

Biochemical pregnancy: Positive βhCG test but no gestational sac is observed on later

transvaginal ultrasound, or menstruation is reported

Spontaneous abortion: Positive \(\beta \) HCG test but all intrauterine gestational sacs are without

fetal heart beat as documented by ultrasound, or there are no

viable fetuses observed by ultrasound

Vanishing twin: Spontaneous disappearance of at least one intrauterine gestational

sac with or without heart beat in a pregnancy where one viable

fetus remains as documented by ultrasound

Ectopic pregnancy: Extrauterine gestational sac with or without fetal heart beat as

documented by ultrasound or surgery

Concerning timing, a pregnancy loss occurring before ongoing pregnancy (i.e. a positive βhCG test but no ongoing pregnancy at 8-9 weeks after transfer) will be defined as an early pregnancy loss, while a pregnancy loss occurring after ongoing pregnancy (i.e. at least one intrauterine viable fetus at 8-9 weeks after transfer but no live birth) during the post-trial follow-up will be defined as a late pregnancy loss.

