3.1 Trial Design

3.1.1 Overall Design and Control Methods

This will be a randomized, double-blind, placebo-controlled, parallel groups, multicenter trial assessing the efficacy and safety of the rFSH preparation FE 999049 in subjects aged 35-42 years undergoing controlled ovarian stimulation for IVF / ICSI following a GnRH antagonist protocol. The primary endpoint is the cumulative ongoing pregnancy rate after the fresh cycle and cryopreserved cycles initiated within 12 months from the start of controlled ovarian stimulation. Thereby, the trial is designed to capture the clinical efficacy of a single controlled ovarian stimulation cycle in a more complete manner by following outcomes from both the fresh and subsequent cryopreserved cycles. Secondary endpoints include pharmacodynamic parameters of FSH action as well as efficacy and safety parameters related to controlled ovarian stimulation from the fresh cycle and subsequent cryopreserved cycles.

Controlled Ovarian Stimulation and Fresh Cycle

Subjects will be screened within 90 days prior to randomization for compliance with the inclusion and exclusion criteria. On day 2-3 of the menstrual cycle, subjects will be randomized in a 10:1 ratio to FE 999049 or placebo, and controlled ovarian stimulation will be initiated. FE 999049 and placebo will be self-administered subcutaneously using a pre-filled injection pen.

Subjects assigned to treatment with FE 999049 will receive a starting dose of 15 µg daily that is fixed for the first four stimulation days. Based on ovarian response, the dose may be adjusted by 3 µg, with dose increases implemented not more frequently than once every 2 days and dose decreases implemented per investigator's judgement. The minimum daily dose is 6 µg, and the maximum daily dose is 24 µg. Subjects assigned to placebo will have the injection pen dialed to the same value (dose) as if administered FE 999049. Subjects can be treated with FE 999049 or placebo for a maximum of 20 days. Coasting, use of dopamine agonist or any other drug to prevent early OHSS with the exception of GnRH agonist for triggering of final follicular maturation, are not allowed.

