3.2 Determination of Sample Size

The proposed sample size of 550 (FE 999049:placebo = 500:50) can adequately address both the efficacy and safety objectives of the trial:

- The cumulative ongoing pregnancy rate in the FE 999049-treated subjects aged 35-42 years is estimated to be approximately 30% according to results from clinical trials conducted in the U.S.¹ By comparison, the pregnancy rate in the placebo arm is expected not to exceed 3%, the monthly spontaneous pregnancy rate in infertile women.² Therefore, the proposed sample size of 550 (FE 999049:placebo=500:50) will provide at least 99% power for the primary efficacy comparison. Based on the estimated cumulative ongoing pregnancy rate, the cumulative live birth rate from the fresh and/or cryopreserved cycles is estimated to be approximately 27%, resulting in a power for the comparison of the cumulative live birth rate to be at least 99%.
- A key pharmacodynamic parameter in subjects aged 35-42 years is cycle cancellation due to poor follicular development, which may occur in approximately 5% of the population exposed to gonadotropins.
- The safety and tolerability of daily rFSH preparations as part of an ART treatment cycle have been well documented for the population studied in previous clinical trials.^{3,4} OHSS was reported to occur in 1.7% to 3.7% of the subjects, with moderate/severe OHSS occurring in 1.4% to 2.2% of the subjects. Other adverse events were pelvic pain, pelvic discomfort and headache, with those assessed to be related to trial treatments reported in 1.5% to 7.1% of the subjects.

Table 1 shows that the planned sample size of 500 subjects exposed to FE 999049 provides a high probability to detect a rare adverse event or safety signal occurring in 0.5% or more subjects.

Incidence rate of rare event	Chance of detecting at least 1 event
0.5%	91.8%
0.6%	95.1%
1%	99.3%

Table 1Probabilities to Detect at Least One Rare Event

Table 2 presents the margin width estimates of the 95% confidence intervals for a range of adverse event rates with the planned sample size.

Adverse event rate	Margin of error width estimate
5%	1.9%
10%	2.6%
15%	3.1%
20%	3.5%

Table 2Estimated Margin Widths of 95% Confidence Intervals

4 Subject Disposition

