9.2 Analysis and Presentation of Primary and Secondary Efficacy Endpoints

Summary tables and treatment comparisons for the primary endpoint will be presented for both the mITT and PP analysis sets. In case that the mITT and ITT analysis sets are not identical (i.e. at least one subject is randomized but not exposed) the summary tables and treatment comparisons will also be presented for the ITT analysis set. As applicable for the secondary endpoints, summary tables and treatment comparisons may be presented for the mITT and PP analysis sets.

All tabulations will be presented by treatment group. Continuous variables will be presented with number of subjects, mean, standard deviation, median, inter-quartile range, minimum, and maximum. Categorical variables will be presented with number and percentage of subjects within each specific category.

All statistical tests will be performed using a two-sided test at a 5% significance level. Treatment differences will (where appropriate) be presented with 95% confidence intervals and p-values corresponding to the statistical test of the hypothesis of 'equal effect' against the alternative of 'different effect'.

Visual displays will be produced as appropriate. All primary and secondary efficacy endpoints will be listed. Listings will only be produced for the mITT.

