10.3.1 Summary Statistics

The circulating levels of clinical chemistry and haematology parameters including change from baseline will be tabulated for each time point for each laboratory variable.

Mean change and mean percentage (%) change from baseline at each time point will be presented for each laboratory variable. In addition, descriptive statistics, i.e., the number of subjects with data, mean (standard deviation), median, minimum, and maximum values, will be presented for observed values and change from baseline at each time point for each laboratory variable.

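### The fresh-cycle adverse event window and end-of-cycle safety time point close at a visit set by pregnancy status, which the crude by-arm displays do not take into account

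*SAP*

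**What the plan says.** Protocol 6.1.12 ties the end-of-cycle visit to the outcome of the cycle. Because of the antibody sampling, "the end-of-cycle assessments can at the earliest be performed 21-28 days after the last FE 999049 or placebo dose"; this is the timing for a canceled cycle, for a cycle without transfer and for a negative βhCG test. Under Protocol 6.1.10, a woman with a positive βhCG test but no vital pregnancy goes on to the visit 35-48 days after transfer. Once vital pregnancy is confirmed, the timing changes again: "the ongoing pregnancy visit will be the last scheduled cycle visit and thus the visit where the end-of-cycle assessments should be done". Protocol 6.1.11 places that visit 56-69 days after transfer.

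SAP 10.2 closes the fresh-cycle treatment-emergent window at this visit and reports the "number of subjects reporting an adverse event, the percentage of subjects with an adverse event, and the number of events reported". Under SAP 10.1 the denominator is every subject in the arm's safety set. The SAP text specifies no person-time rate, common cut-off or pregnancy split. Protocol 8.3.2 makes pregnancy losses part of the count: "The following terminology should be used for reporting of pregnancy losses as adverse events".

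For laboratory values SAP 10.3.1 states: "Mean change and mean percentage (%) change from baseline at each time point will be presented for each laboratory variable". End-of-cycle is handled as a single time point there, in the shift tables of SAP 10.3.2, and for blood pressure and pulse in SAP 10.14.

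**The concern.** Pregnancy is the outcome that the drug is meant to change, so closing the safety window by pregnancy status gives the two arms different observation periods after dosing. The extra weeks are also not like the earlier ones. They cover early pregnancy and, under Protocol 5.1.2, continued luteal progesterone, a co-medication with its own listed reactions in Protocol 1.3.

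The end-of-cycle laboratory and vital-sign tables have the same difficulty. They pool non-pregnant women seen three to four weeks after the last dose with women near the end of the first trimester, most of them on FE 999049.

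Safety is part of the primary objective, and placebo is the only control. What is at stake is how side-by-side percentages are read, including which preferred terms pass the 5% incidence threshold in SAP 10.2.

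**Working it through.** **The plan's own safety figures.** With 500 subjects, 1 - (1 - p)^500 gives 91.8%, 95.1% and 99.3% at 0.5%, 0.6% and 1%. The margin 1.96 × √(p(1 - p)/500) gives 1.9, 2.6, 3.1 and 3.5 points at 5%, 10%, 15% and 20%. Tables 1 and 2 of SAP 3.2 are reproduced. They describe detection and precision within the FE 999049 arm, not the comparison with placebo.

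**Window after the last dose.** Retrieval is 34-38 hours (1.4-1.6 days) after trigger (Protocol 6.1.6) and transfer is 5 days later (6.1.8.1). Assumption: trigger falls 0-1 day after the last dose.
- Canceled cycle, no transfer or negative βhCG: 21-28 days (midpoint 24.5).
- Positive βhCG, no vital pregnancy: 1.4 + 5 + 35 = 41 to 1 + 1.6 + 5 + 48 = 56 days (midpoint 48.5).
- Vital pregnancy: 1.4 + 5 + 56 = 62 to 1 + 1.6 + 5 + 69 = 77 days (midpoint 69.5).

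**Gestation at the end-of-cycle sample.** The dating footnote in Protocol 8.5.1 adds 19 days to the transfer date. This gives 56 + 19 = 75 to 69 + 19 = 88 days, or 10 weeks 5 days to 12 weeks 4 days.

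**Crude percentage with no drug effect.** The model uses a constant hazard h, with F(t) = 1 - exp(-ht). Placebo is taken as having no pregnancies, so its window is stimulation days + 24.5. The documents give no fresh-cycle pregnancy rate for this trial, no stimulation length by arm and no placebo adverse event rate, so all three are assumptions. The vital-pregnancy share is varied from 15% to 35%; the guide is the 26.9% ongoing pregnancy rate at age 35 or over in an earlier phase 3 trial (Protocol 1.1). Earlier losses are varied from 0% to 10%.

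Worked case: 9 stimulation days in both arms, 10% on placebo, 27% vital pregnancy, 5% earlier loss.
- h = -ln(0.9)/33.5 = 0.003145 per day.
- F(33.5) = 10.0%, F(57.5) = 16.5%, F(78.5) = 21.9%.
- FE 999049: 0.27 × 21.9 + 0.05 × 16.5 + 0.68 × 10.0 = 13.5%.
- Mean post-dose window: 0.27 × 69.5 + 0.05 × 48.5 + 0.68 × 24.5 = 37.9 days, against 24.5 on placebo.

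| Vital / earlier loss on FE 999049 | Stimulation days, FE 999049 / placebo | FE 999049 if placebo is 10% | FE 999049 if placebo is 20% |
|---|---|---|---|
| 15% / 5% | 9 / 9 | 12.1% (+2.1) | 23.7% (+3.7) |
| 27% / 5% | 9 / 9 | 13.5% (+3.5) | 26.2% (+6.2) |
| 35% / 10% | 9 / 9 | 14.8% (+4.8) | 28.4% (+8.4) |
| 27% / 5% | 9 / 14 | 11.9% (+1.9) | 23.3% (+3.3) |
| 27% / 5% | 9 / 20 | 10.4% (+0.4) | 20.6% (+0.6) |
| 15% / 0% | 9 / 20 | 9.0% (-1.0) | 18.0% (-2.0) |

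**Events specific to early pregnancy.** If such an event occurs in 30% of vital pregnancies, it adds 0.30 × 15% to 0.30 × 35% = 4.5 to 10.5 points on FE 999049. On placebo it adds at most 0.30 × 3% = 0.9 points. This part does not depend on stimulation length.

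**Sampling noise.** The 95% margin on the difference with 500 and 50 subjects is 1.96 × √(p(1 - p)(1/500 + 1/50)). It is ±8.7 points at 10% and ±11.6 points at 20%.

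**The case against.** The strongest reply is that crude incidence over a visit-bounded window is a recognized choice, and that pregnancy and its consequences belong to the overall effect of treatment. No between-arm safety test is planned: the rule "All statistical tests will be performed using a two-sided test at a 5% significance level" stands in the efficacy section, SAP 9.2. The question is therefore one of interpretation, not of error rate, and the offset is below the noise. This stands and limits the weight of the point.

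A reader might infer that part of any adverse event excess on FE 999049 must come from longer follow-up. The documents do not support that. Protocol 6.1.5 permits cancellation after 8 days or dosing up to day 20, so placebo subjects may be dosed longer. The last two rows of the table show the excess disappearing or changing sign. What is fixed is the longer post-dose period for women who become pregnant.

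A reader might also infer that the planned tables cannot separate these effects at all. That goes too far. The SAP already plans adverse events by investigator causality (10.2), early against late OHSS (10.8), a separate pregnancy-loss table (10.10), injection site reactions confined to stimulation (10.4) and an end-of-stimulation laboratory point before any transfer (10.3). These help in part but leave the general adverse event tables and the end-of-cycle changes as they are. Table shells are a separate document (SAP 15) and may hold more.

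Body weight is not affected in the same way. It is measured at end-of-cycle, but the SAP plans no weight-change table.

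**Conclusion.** The point holds as one of interpretation, of modest size. The documents themselves set the close of the window by pregnancy status, at 21-28 days after the last dose at the earliest against about 62-77 days for a vital pregnancy. They also expect pregnancy in about 30% (cumulatively) against at most 3%. General adverse event percentages and end-of-cycle laboratory and vital-sign changes therefore mix drug effect with post-dose observation time and early pregnancy.

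The direction and size of the net effect on percentages are not fixed. At a 10% placebo base with no drug effect, the offset is roughly +2 to +5 points with equal stimulation length, and nil or negative if placebo dosing runs towards day 20. These figures rest on a constant hazard and on assumed pregnancy shares and stimulation lengths. In every scenario shown the offset is smaller than the sampling margin with 50 placebo subjects. Unlike that noise, it is systematic.

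**What to change.** In SAP 10.2, add a supplementary treatment-emergent overview and a system organ class/preferred term table limited to onset from first dose through 21 days after the last dose. Every subject is scheduled to complete that period, although Protocol 4.4 allows withdrawal at any time. Present events per person-time with it, because the window still varies with stimulation days. Read it alongside the full-window tables when comparing arms, and keep those tables as planned.

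In SAP 10.3 and 10.14, also show fresh-cycle end-of-cycle values by pregnancy status at that visit. Label this display descriptive: the split is made after randomization, and the pregnant placebo cell will hold about 0-2 women (at most 3% of 50 is 1.5).

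The cost is a few extra tables from data already collected. Events after day 21 remain visible only in the full-window tables.

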10.2.1 Overview of Treatment-Emergent Adverse Events and Adverse Events in Cryopreserved Cycles

Adverse events overview summary tables for treatment-emergent adverse events in the fresh cycle and adverse events in cryopreserved cycles will be prepared including the number of subjects reporting an adverse events, the percentage of subjects (%) with an adverse event, and the number of events reported, for the following categories:

- All adverse events
- Severe adverse events
- Adverse drug reactions, defined as adverse events judged by the investigator to be related to IMP with a reasonable possibility
- Adverse events leading to discontinuation
- Serious adverse events
- Deaths

In addition to overview summary tables for the fresh and cryopreserved cycles, an overview summary table for the trial will also be produced.

Ferring Pharmaceuticals

